#### *Severity Assessment*

For purposes of consistency, if required, the investigator may use the severity grades presented in [Table 4](#).

**Table 4: Adverse Event Severity Grades**

Grade	Definition
Grade 1	Mild AE
Grade 2	Moderate AE
Grade 3	Severe AE
Grade 4	Life-threatening AE
Grade 5	Death

Not all grades are appropriate for all AEs. In particular, Grade 5 (Death) is not appropriate for all AEs and therefore will not be considered an option for grading severity of AEs; instead, death, if it occurs, should be recorded as the outcome of a serious AE.

To ensure there is no confusion or misunderstanding of the difference between the terms “serious” and “severe,” which are not synonymous, the following note of clarification is provided:

The term “severe” is used to describe the intensity (severity) of a specific event (as in mild, moderate, or severe myocardial infarction); the event itself, however, may be of relatively minor medical importance (such as a severe headache). This is not the same as “serious,” which is based on the subject/event outcome or action criteria usually associated with events that pose a threat to a subject's life or functioning. Seriousness (not severity) serves as a guide for defining regulatory reporting obligations.

If an AE increases in severity (eg, from moderate to severe); decreases in severity (eg, changes from moderate to mild); or if there is a change in seriousness, a new AE will be opened, and the original AE will be closed. If an AE is still ongoing at the time of a subject’s completion of the Final Visit, the resolution/stop date and time is left blank.

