### 9.5.1. Safety Analyses

For safety variables, 2 observation periods are defined:

- The pretreatment period is defined as the time from signing the ICF until administration of the first dose of study drug.

- The treatment-emergent period is defined as the time from administration of the first dose of study drug to the end of the study.

Treatment-emergent AEs are defined as those that are not present at start of study drug dosing or that represent the exacerbation of a pre-existing condition during the treatment-emergent period.

AEs will be coded using the Medical Dictionary for Regulatory Activities (MedDRA) by preferred term within system organ class. The number of AEs and the number of subjects reporting AEs will be listed and summarized descriptively by body system, preferred term, severity, and causality for each treatment group. Both pretreatment and treatment-emergent AEs (events that are new in onset or aggravated in severity following treatment) will be included in all summaries. SAEs (including death) will be summarized. Treatment-emergent AEs leading to permanent treatment discontinuation will be listed and summarized by treatment group.

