#### 10.3.4. Adverse Event and Serious Adverse Event Recording and Reporting

AEs and SAEs will be recorded from signing of the ICF through completion of the final visit. The investigator is required to record the AE or SAE regardless of the severity of the event or its relationship to study treatment. The investigator must follow up on all AEs and SAEs reported to have occurred through the final visit until the event has resolved or stabilized or at such time the investigator refers the subject to a nonstudy physician. The investigator will document the further follow-up information in the subject’s source document.

During the period specified above, the investigator will:

- Record all AEs and SAEs from the signing of the ICF through the completion of the final visit.
- Report all SAEs on an SAE Report Form to Mallinckrodt Global Pharmacovigilance or designee.
- Report all pregnancies to Mallinckrodt Global Pharmacovigilance or designee on the appropriate form.
- Submit any Expedited Safety Report or Suspected Unexpected Serious Adverse Reaction from Mallinckrodt Global Pharmacovigilance or designee to the IRB/IEC.

The reporting requirements for AEs are summarized in [Table 5](#).

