### 10.3.5. Adverse Events of Special Interest

An AESI is an event of scientific and medical concern specific to the sponsor's product or program, for which ongoing monitoring and rapid communication by the investigator to the sponsor can be appropriate. Such an event might warrant further investigation in order to characterize and understand it. These will be reported on the AE form including start date and time, stop date and time, severity, relation to study drug, any action taken with the study drug, and outcome of the event.

CNS or abuse-related AEs will also be considered as AESIs for this study, based on the recommendation of the FDA to closely monitor these events and report time of onset, duration of the event, dose of drug taken, severity, and outcome. The eCRF page for these AESIs will be designed to capture the above data points. Narratives for all AESIs will be prepared from the data reported on the eCRFs. PK values for each individual subject who experienced these AEs will be provided to understand if there is a temporal correlation between drug plasma levels and AEs.

CNS AESIs include somnolence, fatigue, lightheadedness, headache, dysgeusia, hypoacusis, disorientation, impaired memory, peripheral neuropathy, euphoria, impaired cognition, attention, mood, psychomotor effects, inappropriate affect, and aberrant behavior.

The following are the abuse-related AESIs: abuse, overuse, lost/stolen/missing or unaccounted product, any aberrant behavior in subjects who drop out of the study supposedly due to lack of efficacy, lost to follow-up, noncompliance or overcompliance. Also, any use of a study treatment by individuals other than enrolled subjects need to be reported, if any.

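### Splitting an AE record at every change in severity or seriousness, with no stated rule to link the pieces, inflates event counts and restarts the onset and duration of CNS AESIs

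*Combined protocol and SAP*

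**What the plan says.** **Recording.** Section 10.3.4 states that "AEs and SAEs will be recorded from signing of the ICF through completion of the final visit", so AEs that begin before the first dose exist as records. The text under Table 4 in Section 10.3.3 says what happens when an AE changes: if it "decreases in severity (eg, changes from moderate to mild); or if there is a change in seriousness, a new AE will be opened". An increase in severity is handled the same way. In each case the earlier record ends at that point ("and the original AE will be closed"). No parent record, episode identifier or collapsing rule is described.

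**Analysis.** Section 9.5.1 says "Treatment-emergent AEs are defined as those that are not present at start of study drug dosing". A second limb of the definition brings in AEs "that represent the exacerbation of a pre-existing condition during the treatment-emergent period". The section then restates the idea as "events that are new in onset or aggravated in severity following treatment". Both the number of AEs and the number of subjects with AEs are to be tabulated, by severity and causality among other factors. On scope, it says: "Both pretreatment and treatment-emergent AEs (events that are new in onset or aggravated in severity following treatment) will be included in all summaries".

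**AESIs.** For CNS and abuse-related events, Section 10.3.5 cites an FDA recommendation to "closely monitor these events and report time of onset, duration of the event, dose of drug taken, severity, and outcome". Narratives are to be prepared from the eCRF data, and individual PK values are to be supplied to look for a relation in time between plasma levels and events.

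**The concern.** The recording rule and the analysis use different units. Section 10.3.3 makes each severity stage its own AE. The event counts in Section 9.5.1 and the onset and duration items in Section 10.3.5 are only meaningful for a whole episode, and nothing supplied turns one into the other.

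Three outputs are exposed:

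- **Event counts.** A subject whose event eases in steps contributes several AEs, one in each severity row, where a subject whose event stops abruptly contributes one.
- **AESI timing.** The start time on a later record can be the time at which an event eased. Set against plasma phenylacetate, that time says nothing about what provoked the event. Phenylacetate exposure and neurotoxicity is a listed secondary endpoint (Section 3.2).
- **Treatment-emergent status, depending on how it is programmed.** A record opened after the first dose because a pre-dose event improved has a post-dose start date. A derivation that looks only at that date would flag it.

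**Working it through.** The plan states no figure to reproduce on this point. The check applies its rules to example records; the times and grades are assumed for illustration.

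**1. Event count and AESI timing (follows from the text as written).** A CNS AESI is severe 10:00-12:00, moderate 12:00-15:00 and mild 15:00-20:00.

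| | Split as in 10.3.3 | One episode |
|---|---|---|
| AEs counted | 3 | 1 |
| Onset | 10:00, 12:00, 15:00 | 10:00 |
| Duration | 2, 3 and 5 h | 2 + 3 + 5 = 10 h |
| Mean duration per record | 10/3 = 3.3 h | 10 h |

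Each change of grade adds one to the event count and one onset.

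**2. Comparison with plasma levels.** Section 8.5.2.1 samples plasma before the first dose on Day 1, then just before and 1 hour after the last dose on Days 1, 3 and 5. Section 6.1 places the last dose at 6 PM, so the post-dose sample falls at about 18:00 + 1 h = 19:00. Suppose somnolence starts at 14:00 and eases at 19:00. The records show onsets at 14:00 and 19:00. The second coincides with the post-dose sample, although the subject was improving.

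**3. Treatment-emergent status (depends on the derivation).**

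| Event | From record start date | From linked episode, worsening only |
|---|---|---|
| Moderate on Day -10, mild on Day 2 | second record flagged | not flagged |
| Mild before dosing, severe on Day 3 | second record flagged | flagged |

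The two derivations agree when an event worsens and disagree when it improves. The definition in Section 9.5.1 names absence at dosing, or exacerbation. An event present at dosing that eases meets neither, so the linked result is the one that matches the definition.

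**4. Scale.** Section 9.1 randomizes 48 subjects equally to four groups: 48/4 = 12 per arm. One subject wrongly flagged moves that arm's treatment-emergent rate by 1/12 = 8.3 percentage points, and the pooled MNK6106 rate by 1/36 = 2.8 points. The documents give no frequency for AEs ongoing at first dose or for improvement, so no expected number of such subjects is offered.

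**The case against.** A reader might infer that the plan classifies an improving pre-dose AE as treatment-emergent. It does not. Section 9.5.1 counts a change in severity only when it is a worsening, both in its exacerbation limb and in its restatement. The false flag needs a programmer to rely on the split record's start date alone, which no section prescribes.

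A reader might also infer that the secondary safety endpoint is distorted, or that an arm which relieves symptoms better would look less safe. The documents do not support this either:

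- The endpoint in Section 3.2 and the outcome measure in Section 3.3 are not restricted to treatment-emergent AEs. Section 9.5.1 puts pretreatment AEs in all summaries, so the subject in the first row of the status table already counts as having an AE.
- Conditions already present at screening are recorded as medical history (Section 8.6.1). The mechanism reaches only AEs that begin after consent, are ongoing at first dose and then ease without resolving.
- A difference between arms would need assumed rates of ongoing and improving events, which the documents do not give.

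Further, Section 9.5.2 refers to a statistical analysis plan whose text is not among the documents reviewed, and the eCRF is not supplied. Either could contain a linking rule. Section 10.3.5 says the AESI page will be designed to capture the duration of the event. Split records keep dated grades, so episodes can be rebuilt and no data are lost. The study is exploratory and its AE summaries are descriptive.

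All of this stands, and it limits the point to event counts, AESI onset and duration, and a conditional risk to treatment-emergent status. It does not remove the first two. There the plan states a rule, and following it produces the fragmented figures.

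**Conclusion.** The concern holds in a limited form. Applied as written, Section 10.3.3 counts one event that changes grade as several AEs in the tables of Section 9.5.1, and restarts onset and duration at each change for the CNS AESIs of Section 10.3.5. In the worked example, one event of 10 hours becomes three of 2, 3 and 5 hours. This needs no assumption beyond the absence of a linking rule in the documents reviewed.

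The treatment-emergent error is conditional on status being derived from record start dates. Where it occurs, one subject is 8.3 points in an arm of 12, but the number of subjects with any AE does not change. How often it would occur cannot be estimated from the documents. If the separate analysis plan or the eCRF already links the records, a cross-reference is enough.

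**What to change.** 1. **Section 9.5.1.** Derive treatment-emergent status and event counts per linked episode. An episode is treatment-emergent if its onset is at or after the first dose, or if any post-dose grade is higher than the grade at first dose. State that a record opened only because severity or seriousness decreased inherits the onset and status of the event it continues. Say also how a pre-dose event that becomes serious after dosing with no rise in grade is to be classed.
2. **Section 10.3.3.** Link each split record to the event it continues, through a parent-event field on the eCRF or by matching term and contiguous dates.
3. **Section 10.3.5.** Take AESI onset from the first linked record, and duration from the first start to the last stop. Keep the dated grades in the listings, so that the time of a worsening can still be set against plasma levels.

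The cost is protocol or analysis plan wording, one eCRF field (none if linking is by term and dates) and some programming. No subjects, visits or procedures are added.

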#### 10.3.4. Adverse Event and Serious Adverse Event Recording and Reporting

AEs and SAEs will be recorded from signing of the ICF through completion of the final visit. The investigator is required to record the AE or SAE regardless of the severity of the event or its relationship to study treatment. The investigator must follow up on all AEs and SAEs reported to have occurred through the final visit until the event has resolved or stabilized or at such time the investigator refers the subject to a nonstudy physician. The investigator will document the further follow-up information in the subject’s source document.

During the period specified above, the investigator will:

- Record all AEs and SAEs from the signing of the ICF through the completion of the final visit.
- Report all SAEs on an SAE Report Form to Mallinckrodt Global Pharmacovigilance or designee.
- Report all pregnancies to Mallinckrodt Global Pharmacovigilance or designee on the appropriate form.
- Submit any Expedited Safety Report or Suspected Unexpected Serious Adverse Reaction from Mallinckrodt Global Pharmacovigilance or designee to the IRB/IEC.

The reporting requirements for AEs are summarized in [Table 5](#).

**Table 5: Reporting Requirements for Adverse Events**

Seriousness	Reporting Time	Type of Report
All Serious	Within 24 hours of first knowledge of event	Initial report on the SAE Form, appropriate eCRF, and source document
	Within 24 hours of receipt of follow-up information	Follow up report on the SAE Form, appropriate eCRF, and source document

**Table 5: Reporting Requirements for Adverse Events (Continued)**

Seriousness	Reporting Time	Type of Report
Nonserious	Per case report form submission procedure	Appropriate eCRF and source document

### 10.3.5. Adverse Events of Special Interest

An AESI is an event of scientific and medical concern specific to the sponsor's product or program, for which ongoing monitoring and rapid communication by the investigator to the sponsor can be appropriate. Such an event might warrant further investigation in order to characterize and understand it. These will be reported on the AE form including start date and time, stop date and time, severity, relation to study drug, any action taken with the study drug, and outcome of the event.

CNS or abuse-related AEs will also be considered as AESIs for this study, based on the recommendation of the FDA to closely monitor these events and report time of onset, duration of the event, dose of drug taken, severity, and outcome. The eCRF page for these AESIs will be designed to capture the above data points. Narratives for all AESIs will be prepared from the data reported on the eCRFs. PK values for each individual subject who experienced these AEs will be provided to understand if there is a temporal correlation between drug plasma levels and AEs.

CNS AESIs include somnolence, fatigue, lightheadedness, headache, dysgeusia, hypoacusis, disorientation, impaired memory, peripheral neuropathy, euphoria, impaired cognition, attention, mood, psychomotor effects, inappropriate affect, and aberrant behavior.

The following are the abuse-related AESIs: abuse, overuse, lost/stolen/missing or unaccounted product, any aberrant behavior in subjects who drop out of the study supposedly due to lack of efficacy, lost to follow-up, noncompliance or overcompliance. Also, any use of a study treatment by individuals other than enrolled subjects need to be reported, if any.

### 10.4. Pregnancy Reporting

Certain information regarding pregnancy, although not considered an SAE, must be recorded, reported, and followed up as indicated. This includes the following:

Subjects should not become pregnant during the study. If a female subject, or the female partner of a male subject, becomes pregnant during any active treatment period, study treatment must be discontinued immediately and the investigator must report the pregnancy by submitting the appropriate form to Mallinckrodt Global Pharmacovigilance, or designee, within 24 hours of confirmation of a pregnancy (ie, positive serum pregnancy test result). The outcome of pregnancy (eg, spontaneous abortion, live birth, still birth, congenital anomalies, birth defects) must be reported by submitting the appropriate form to Mallinckrodt Global Pharmacovigilance, or designee, within 24 hours of the pregnancy outcome being submitted to the study site. If the pregnancy results in a live birth, a post-delivery follow-up will be performed at least 28 days

---

after the baby is born and must be reported to Mallinckrodt Global Pharmacovigilance, or designee, within 24 hours of the study site becoming aware of the follow-up information.

### **10.5. Liver Safety: Suggested Actions and Follow-up Assessments**

All events of alanine aminotransferase at least  $3 \times$  the upper limit of normal (ULN) and with total bilirubin at least  $2 \times$  ULN (greater than 35% direct bilirubin) or alanine aminotransferase at least  $3 \times$  ULN and INR greater than 1.5 (if INR is measured) which may indicate severe liver injury must be reported as an SAE as outlined in Section 10.3.4 (excluding studies of hepatic impairment or cirrhosis).

In subjects with cirrhosis and elevated transaminases and bilirubin at baseline, subjects should be discontinued if their alanine aminotransferase or total bilirubin level doubles, or if they develop new symptoms suggestive of drug induced liver injury (jaundice, malaise, abdominal pain, unexplained nausea and anorexia) or decompensation events during the study.

### **10.6. Clinical Function Scoring**

#### **10.6.1. Conn Score**

Subjects will be assessed at screening and every day using the Conn score, to determine if they have a worsening in HE, indicated as an increase in their score by 1 or more grades. The Conn score (also known as the West Haven Criteria) is an extensively used grading scale for assessment of HE severity. It consists of a 5-point scale (Grade 0 to 4) as follows:

- Grade 0: no apparent personality or behavioral abnormality;
- Grade 1: trivial lack of awareness, euphoria or anxiety; shortened attention span; impairment of addition or subtraction;
- Grade 2: lethargy; disorientation for time; obvious personality change; inappropriate behavior;
- Grade 3: somnolence to semi-stupor, responsive to stimuli; confused; gross disorientation; bizarre behavior;
- Grade 4: coma; unable to test mental state.

#### **10.6.2. HESA Score**

The HESA score will be assessed at the screening visit to assess study eligibility, and will also be assessed on Days 1 through 5/ET, to determine if subjects have a worsening in their condition. The HESA implements objective ways of measuring the parameters of the West Haven scale. The HESA utilizes clinical indicators combined with validated neuropsychological tools and well-defined criteria for each stage (see HESA algorithm in Section 10.8). The use of the HESA is still limited and its metric characteristics have not been fully analyzed. One favorable characteristic of the HESA is that it identifies low grades of HE precisely. It consists of a 5-point scale (Grade 0 to 4), with 4 indicating most severe ([Hassanein et al, 2008](#)).

### 10.6.3. MELD Score

Subjects will be assessed at the screening visit to assess eligibility into the trial. Additionally, subjects will be assessed at each visit using the MELD score, to determine if they have a worsening in their condition. MELD is a scoring system for assessing the severity of chronic liver disease. It was initially developed to predict mortality within 3 months of surgery in patients who had undergone a transjugular intrahepatic portosystemic shunt procedure and was subsequently found to be useful in determining prognosis and prioritizing for receipt of a liver transplant. MELD uses the patient's values for serum bilirubin, serum creatinine, and the INR for prothrombin time to predict survival. It is calculated using the following formula:

$$\text{MELD} = 3.78 \times \ln[\text{serum bilirubin (mg/dL)}] + 11.2 \times \ln[\text{INR}] + 9.57 \times \ln[\text{serum creatinine (mg/dL)}] + 6.43$$

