### 2.1. Background

Although the onset of HE can rarely be pinpointed clinically, it is a landmark in patients with advanced liver disease ([Wijdicks, 2016](#)). An estimated 60% to 70% of cirrhotic patients have at least subtle signs of neurocognitive impairment. Overt HE has a prevalence of approximately 30% in patients with end-stage liver disease, and accounts for about 150,000 hospitalizations annually in the United States ([Al Sibae et al, 2009](#)). Severe HE in patients with cirrhosis is associated with a mortality of more than 50% in the first year alone ([Wijdicks, 2016](#)).

HE is a neuropsychiatric disorder that occurs when gut derived toxins, primarily AMM, bypass a failing liver, which would normally detoxify such agents. These toxins enter the circulation and cross the blood brain barrier, resulting in impairment of neurotransmission and central nervous system (CNS) function. HE can arise in the setting of acute liver failure, chronic progressive liver disease in the context of advanced liver cirrhosis (overt HE), and/or as a result of portocaval shunting with or without liver disease. The pathogenesis of HE has been incompletely understood but the increase in plasma AMM levels remains central to the understanding of HE ([Wijdicks, 2016](#)), supporting the need for novel, safe, and effective AMM lowering therapies to treat as well as to prevent episodes of HE.

Dietary protein restriction had long been advocated as a strategy to reduce circulating AMM in patients with cirrhosis. However, recent data have shown that this strategy is not effective in preventing HE and may harm these patients by making them more prone to muscle wasting ([Cordoba et al, 2004](#)).

---

---

Current treatment guidelines for episodic overt HE recommend lactulose, a non-absorbed disaccharide, at a dose of 25 mL twice daily as first line agent, adjusted for the production of 3 bowel movements daily ([American Association for the Study of Liver Diseases, 2014](#)). Rifaximin, which alters gut microbiota, is recommended as an add-on therapy to lactulose for prevention of HE recurrence ([American Association for the Study of Liver Diseases, 2014](#)); ([Wijdsicks, 2016](#)). However, recent data suggest that a significant number of patients receiving lactulose and rifaximin are hospitalized with a recurrence of HE ([Kulkarni et al, 2018](#)).

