## 5.2. Exclusion Criteria

A subject is ineligible for study participation if, at the Screening Visit, the subject:

1. Is from a vulnerable population, as defined by the US Code of Federal Regulations (CFR) Title 45, Part 46, Section 46.111(b) and other local and national regulations, including but not limited to, employees (temporary, part-time, full time, etc.) or a family member of the research staff conducting the study, or of the sponsor, or of the contract research organization, or of the Institutional Review Board (IRB)/Independent Ethics Committee (IEC).
  2. Has a history of sensitivity or allergy to MNK6106, ORN, PAA, L-ornithine L-aspartate, phenylbutyrate or rifaximin.
  3. Has expectation of liver transplantation within 1 month after the Screening Visit.
  4. Had placement of a portosystemic shunt or transjugular intrahepatic portosystemic shunt within 3 months before the Screening Visit.
  5. Has a Model for End Stage Liver Disease (MELD) score greater than 25.
  6. Has HESA score Grade 4.
  7. Had gastrointestinal bleeding within 3 months of the Screening Visit.
  8. Has severe renal impairment (Creatinine Clearance rate no more than 30 mL/min) calculated using the Cockcroft-Gault formula.
  9. Has intercurrent infection or active spontaneous bacterial peritonitis.
  10. Has known immune compromised status (not related to disease/condition under study), including but not limited to individuals who have undergone organ transplantation or who are known to be positive for the human immunodeficiency virus (HIV).
  11. Has any solid tumor malignancy currently diagnosed or undergoing therapy or has received therapy for any solid tumor malignancy in the 5 years prior to the Screening Visit; with the exception of treated and cured basal cell carcinoma, treated and cured squamous cell carcinoma of the skin, and treated and cured carcinoma in situ of the cervix.
  12. Has a history of prior cognitive impairment.
  13. Has a history of psychotic disorders including but not limited to schizophrenia, dementia, or other severe psychotic disorders that would interfere with evaluation of HE.
  14. Has a positive screening result for drugs and alcohol (except for subjects positive to cannabinoids).
-

- 
15. Has a QT interval corrected using Fridericia's Formula (QTcF) of at least 500 msec at screening.
  16. Has any of the following laboratory abnormalities at the Screening Visit:
    - Hemoglobin < 8.0 g/dL.
    - Platelet count < 25,000 cells/ $\mu$ L.

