## 9.5. Other Analyses

Summary statistical analyses will be provided for demographics, medical history, physical examination, social history, and risk factor variables at baseline.

For C-P, MELD, Conn, and HESA scores:

- The change and percent change of C-P, MELD, Conn, and HESA scores by visit will be summarized and analyzed using multiple imputation with an analysis of covariance model, respectively.
- The percent of subjects with C-P (A, B, C), MELD (40+, 30-39, 20-29, 10-19, <9), Conn (0,1,2,3,4) and HESA (0,1,2,3,4) will be provided by treatment group and by visit, respectively.
- The percent of subjects with improvement vs no change from baseline in the C-P category, MELD category based on category of 40+, 30 to 39, 20 to 29, 10 to 19, < 9, Conn and HESA will be analyzed by the Cochran–Mantel–Haenszel test stratified by baseline category, respectively.

The graphics for the 4 scores by treatment and by visit will be presented.

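### MELD is computed from logged laboratory values with no minimum, so scores can be near zero or negative and the planned percent change in MELD breaks down at low baselines

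*Combined protocol and SAP*

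**What the plan says.** Section 10.6.3 defines MELD as 3.78 × ln(bilirubin, mg/dL) + 11.2 × ln(INR) + 9.57 × ln(creatinine, mg/dL) + 6.43. It says that "MELD uses the patient's values for serum bilirubin, serum creatinine, and the INR for prothrombin time to predict survival". It gives no minimum for any input, no minimum for the score and no rounding rule, and no other section supplies one. Section 9.5.2 mentions a statistical analysis plan, but only for exposure periods.

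The score has three uses:

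- **Entry.** Section 5.2, exclusion 5, removes a subject who "Has a Model for End Stage Liver Disease (MELD) score greater than 25". Section 10.6.3 says that MELD is assessed at screening for eligibility.
- **Change over time.** Section 9.5 plans an ANCOVA for each score: "The change and percent change of C-P, MELD, Conn, and HESA scores by visit will be summarized and analyzed using multiple imputation". Table 1 schedules MELD at screening, on Days 1 to 6 and at the final visit.
- **Categories.** Section 9.5 uses the classes "MELD (40+, 30-39, 20-29, 10-19, <9" and tests improvement against no change with a Cochran–Mantel–Haenszel test.

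**The concern.** The logarithm of a value below 1.0 is negative. A creatinine or bilirubin below 1.0 mg/dL therefore takes points off, and nothing stops the total from reaching zero or less. A percent change needs a baseline that is positive and well away from zero. If the baseline is close to zero the percentage becomes very large. If it is negative the sign reverses, and a rising (worsening) score is reported as a percentage decrease.

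Two lesser consequences follow from the same formula. A small creatinine movement below 1.0 can carry a subject across a MELD class boundary and so enter the improvement test. A low creatinine can also offset high bilirubin and INR in exclusion 5.

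A further practical risk is inconsistency. A site or programmer who applies a private minimum will get a different score from the same laboratory values than one who follows the text exactly.

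**Working it through.** The plan gives no worked MELD value, so there is no figure to reproduce. The formula and cut-offs come from Sections 10.6.3, 5.2 and 9.5. All laboratory values below are assumed for illustration. The comparison sets any input below 1.0 to 1.0. That minimum is also an assumption: it is the value at which each log term is zero.

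**1. Points subtracted as written.** 9.57 × ln(creatinine) at 0.8, 0.7, 0.6 and 0.5 is -2.14, -3.41, -4.89 and -6.63. 3.78 × ln(bilirubin) at 0.8, 0.7 and 0.5 is -0.84, -1.35 and -2.62.

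**2. Where the score reaches zero.** With bilirubin 1 and INR 1, MELD = 0 at creatinine exp(-6.43/9.57) = 0.51. With bilirubin 0.5 and INR 1.1 it is 0 at creatinine 0.60. With bilirubin 2 and INR 1.5 this happens only at 0.24. Bilirubin 0.6, INR 1.0, creatinine 0.5 gives -2.13.

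**3. Percent change when only creatinine moves.**

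| Bilirubin, INR | Creatinine | MELD as written | Percent change | With minimum 1.0 |
|---|---|---|---|---|
| 0.7, 1.1 | 0.5 to 0.6 | -0.48 to 1.26 | about -360% | 7.50 at both, 0% |
| 1.0, 1.1 | 0.5 to 0.6 | 0.86 to 2.61 | about +202% | 7.50 at both, 0% |
| 0.8, 1.1 | 0.6 to 0.7 | 1.77 to 3.24 | about +84% | 7.50 at both, 0% |
| 2.5, 1.5 | 0.7 to 0.8 | 11.02 to 12.30 | +11.6% | 14.43 at both, 0% |

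First row: -1.35 + 1.07 - 6.63 + 6.43 = -0.48, and -1.35 + 1.07 - 4.89 + 6.43 = 1.26. The change of about 1.74 divided by -0.48 is about -360% (unrounded inputs). Section 9.1 gives 48/4 = 12 subjects per arm. If the other 11 had 0% change, this one subject would set the arm mean at -360/12 = -30%, although the only subject who changed got worse.

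**4. Category shift.** Bilirubin 2, INR 1.4: creatinine 0.6 gives 2.62 + 3.77 - 4.89 + 6.43 = 7.93 (lowest class), and 0.8 gives 10.68 (class 10-19). A fall from 0.8 to 0.6 would count as a category improvement with bilirubin and INR unchanged. With the minimum, both score 12.82.

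**5. Exclusion 5.** Bilirubin 15, INR 2.5, creatinine 0.6 scores 10.24 + 10.26 - 4.89 + 6.43 = 22.04 and is not excluded. Bilirubin 12, INR 2.3, creatinine 1.0 scores 9.39 + 9.33 + 0 + 6.43 = 25.15 and is excluded, although both its bilirubin and its INR are better. With the minimum the first subject scores 26.93.

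**6. How often.** Simulation with assumed lognormal values: medians of bilirubin 1.5 to 3, INR 1.3 to 1.6 and creatinine 0.8 to 0.9; log-scale SDs of 0.6, 0.2 and 0.35; INR not below 0.9.

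- MELD at or below 0: about 0.1% to 2.7% of subjects.
- MELD within 2 points of zero: about 0.3% to 6%, or roughly 0.1 to 2.9 of 48.
- Not excluded solely because there is no minimum: about 0.1% or less, or about 0.05 of 48.
- At least one input below 1.0: about 63% to 82%.

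**The case against.** The case for leaving the text alone has real weight.

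- **Low stakes.** MELD is not a primary or secondary endpoint in Sections 3.1 and 3.2, and Amendment 2 removed changes in these scores from the secondary endpoints. The study is exploratory with no hypothesis to test. This stands, and it limits the weight of the point.
- **Absolute change is already planned.** This is true, and it makes percent change easy to drop. It does not make the percent-change analysis valid.
- **Few subjects have baselines near zero.** This also stands: at an ordinary baseline the effect is about 12%, as in the last row of the table. With about 12 per arm, however, one extreme value is enough.
- **A minimum does not stop creatinine moving MELD.** With the minimum applied, bilirubin 0.8 and INR 1.1, creatinine 1.0 to 1.2 still adds 9.57 × ln(1.2) = 1.74 points (7.50 to 9.24, +23%). This is correct, and it is a further reason to prefer absolute change.

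Three stronger readings are tempting but not supported.

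- A reader might infer that the protocol itself describes the enrolled subjects as muscle-wasted and so likely to have low creatinine. Section 2.1 says that dietary protein restriction "may harm these patients by making them more prone to muscle wasting". That concerns a diet strategy and says nothing about creatinine or the enrolled population. It is true only that no criterion limits low creatinine: the renal criterion, "Has severe renal impairment (Creatinine Clearance rate no more than 30 mL/min", acts in the other direction.
- A reader might infer that exclusion 5 lets in sicker subjects in meaningful numbers. The estimate above is about 0.05 of 48, and exclusion 17 lets the investigator exclude for any clinically significant abnormality.
- A reader might infer that every subject whose score with the minimum exceeds 25 is wrongly admitted. That depends on rounding too: a score between 25 and 25.5 would round to 25 and not be excluded.

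**Conclusion.** The point holds, with its weight on the percent-change analysis. Followed exactly, Section 10.6.3 yields scores near or below zero, and percent change in MELD is then unstable or has the wrong sign. Category shifts driven by low-range creatinine alone are a second, smaller effect and need no extreme values. Reversed ordering around exclusion 5 is possible but very rare.

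The arithmetic follows directly from the stated formula. The laboratory values and distributions are assumptions, so the frequencies are only indicative, and the minimum of 1.0 is not given in the documents. A reader might infer that the study's main result is at risk. It is not: the ammonia endpoint does not use MELD. This is a worthwhile, inexpensive correction to a supporting analysis.

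**What to change.** 1. In Section 9.5, drop percent change in MELD and keep absolute change.
2. In Section 10.6.3, state a minimum for each log input and a rounding rule. A minimum of 1.0 is a natural choice because each log term is zero there, but the sponsor must choose and state it. At 1.0 the unrounded score cannot fall below 6.43.
3. Derive MELD by that one rule for all Section 9.5 analyses. The sponsor should confirm that exclusion 5 uses the same derivation.

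The cost is one or two sentences and a line of programming. Creatinine movement below the minimum would no longer show in the score. Under the assumed distributions most subjects have at least one input below 1.0, so many scores would rise somewhat. A very small number of subjects could change eligibility.
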